Families will be recruited from pediatric practices in our Practice-based Research Networks (PBRNs) in several ways. Each practice will have children who meet age, height, and weight criteria flagged in their charts, and we will use multiple approaches to recruit families. First, we will establish a ResearchMatch approach to recruiting in each PBRN. ResearchMatch, an online recruitment tool, will accrue families in one of two ways. At intake for a well- or sick-child visit, forms designed to acquaint families with the study will be introduced by PLAN coaches, and families can sign up for additional information about this study. Their information will be entered into a database by the PLAN coaches, and they will be contacted if they meet criteria. In addition, we will set up a website that they will be directed to in a flyer, and they can sign up to participate from the website. Since the pediatrician generally will not have information on parental health, this will need to be collected prior to deciding study eligibility, and the family database will assist in this endeavor by including information about all family members after a phone screen is conducted by the PLAN coaches with the participating parent. Second, PBRN practices post study advertisement at offices for interested families to visit the study website to complete questionnaires to ensure they meet eligibility criteria. If the families meet eligibility criteria, a PLAN coach will follow up with the families to schedule their first appointment at their earliest convenience. At this appointment, the PLAN coach will confirm the families' interest to participate and eligibility prior to participation. Third, Plan coaches will meet with families during well-child visits to introduce the study, assess their interest, and explain next steps. Each of these methods in collecting their information regarding interest and eligibility will be preceded by getting their verbal consent over the phone or a check box indicated on the web pages.

During recruitment, PLAN coaches will explain that there is a 50/50 possibility of getting one treatment over the other treatment. This will be like a flip of the coin and no one can just pick one treatment or the other. This study is testing if the FBT is as good as the care provided by their doctors normally given or better. Randomization will occur after the first appointment.

Inclusion Criteria

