The DCC will organize annual site visits to all clinics that will focus on a detailed review of study procedures. Special additional site visits may occur if routine quality control measures determine that a clinic is having difficulty with some aspect of the protocol. Site visitors will prepare an agenda that will include observations of the performance of study procedures and of the filing system that is used to store completed data forms. They will confirm that data forms are correctly filed, that IRB approvals are available, and that changes on forms are appropriately initialed and dated by the person who made the changes. In addition, site visitors may do random data audits in accordance with section **X.F.2**. Site visits will generally be conducted by a DCC staff person and by an investigator from another clinic.

III. Statistical Considerations

A. Statistical Analysis Plan

Data will be analyzed with SAS using the intention-to-treat principle. P-values less than 0.05 will be considered significant and all tests are two-sided. Details of how the intention-to-treat principle will be implemented are contained in a later section.

B. Primary Analysis

The primary goal of this study is to determine whether the change in weight status among children who have overweight/obesity (*Primary Specific Aim 1, DSMB approved protocol addenda, 11.2.18*) is superior among those who are randomized to family-based treatment (FBT) as compared to those who are randomized to usual care (UC) when treated in a primary care setting. The primary outcome measure in children is the percent over the age- and sex-specific 50th BMI percentile. The specific question of interest in the primary analysis is whether the change from baseline to 24 months in the intervention group is greater in the FBT group than in the UC group.

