The primary analytic strategy reflects the fact that this is an individually randomized group treatment (IRGT) trial.³⁴ An IRGT trial is one in which the individual, in this case the family, is the unit of randomization. It differs from a classic individually randomized trial in that the intervention is either a group intervention or, alternatively, is conducted by an agent who is responsible for implementing the intervention in a defined set of individuals. In PLAN, participants are randomized at the family level and only one randomly chosen eligible child (the index child) is included in the primary analysis. The intervention is conducted by a coach who assumes responsibility for a set of families that receive individualized interventions. Since the study has four sites with three coaches per site, the analysis plan involves a nesting of the coach within the site. *Some sites have backup and floating coaches that are involved in delivering FBT to study participants, which will also be accounted for when outcome data is analyzed (This change was made on 12.4.18 prior to review and approval by the DSMB, DSMB approved protocol addenda on 11.18.19)*. While this nesting suggests a classic cluster randomized trial, an IRGT trial is different because the nesting applies only to the intervention group. Since the control group, in this case the UC group, has no nesting factor in an IRGT trial, a proper analysis must reflect the fact that in an IRGT trial, the intervention group and the control group must use different covariance structures.

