With the above comments in mind and with the focus of the study being on a between-group comparison of the change from baseline to 24 months, the primary analysis will be an analysis of covariance with the 24-month value as the dependent variable and with the baseline value as a predictor variable. The statistical model we employ reflects the parametrization described by Baldwin and Colleagues.⁶⁰ It takes the initial form $Y_{24ij} = \beta_{0j} + \beta_{1j}X_{ij} + Y_{0ij} + e_{ij}$. In this model, Y_{24ij} is the 24-month value of the percent over the age and sex matched 50th BMI percentile (the primary outcome) for subject i and cluster j , with the “clusters” being defined by the coach in the intervention group and by individual children in the control group; β_{0j} and $\beta_{1j}X_{ij}$ are the intercept and intervention effect for cluster j ; Y_{0ij} is the baseline value of the outcome measure; and e_{ij} is the normally distributed error term. *In these models, the intercept and baseline are fixed effects while the intervention effect is random (DSMB approved protocol addenda, 11.2.18).* To reflect the partial clustering structure of the IRGT design, the above expression is modified by using the cluster-level equations $\beta_{0j} = \lambda_{00}$ and $\beta_{1j} = \lambda_{10} + \mu_{1j}$ to describe how the coefficients β_{0j} and β_{1j} vary across clusters. *The reparametrization of β_{1j} yields two random effects (DSMB approved protocol addenda, 11.2.18)* and the term μ_{1j} permits between-cluster variability in the outcome measure only within the intervention group (coded as 1). Substituting in the initial equation above yields the final model:

$$Y_{24ij} = \lambda_{00} + \lambda_{10}X_{ij} + \mu_{1j} X_{ij} + Y_{0ij} + e_{ij}$$

Using PROC MIXED in SAS, separate covariance structures will be fit to the FBT group and the UC group to account for the fact that the coach is nested within the site in the FBT group while there is no such nesting in the UC group. All analyses other than the above are secondary or exploratory analyses. One of those secondary analyses will supplement the primary analysis by adjusting for the sex and race of the participating child, family income, the educational level of the participating parent, and whether there are one or two parents in the household. These secondary analyses will provide insight regarding the impact the covariates may have on the primary outcome.

1. Sample Size and Statistical Power

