Power computations for PLAN employ simulations and two-sided tests at the 0.05 level of significance. The simulations reflect the planned primary analysis of covariance and the fact that this is an individually randomized group treatment trial with the coach (N=3 per site) nested within the site (N=4 sites) in the FBT group but with no such nesting in the UC group. The analysis of covariance that is simulated in the power computations treats the 24-month value of the outcome measure as the dependent variable and the baseline value as a covariate. The use of this approach reflects the primary study goal of comparing 24-month values across groups, with the outcome being compared being percent over normalized BMI in the participating child. Each result is based on 1000 simulations.

Tabulated power values employ sample sizes of 528 and that are between 65% and 95% of that total. Effect size estimates are generated using considerations and preliminary data discussed below. Usual care data involving an intervention and subjects most similar to our UC group is provided by Kalarchian⁶¹ who randomized 81 8-12-year-old children with obesity to a usual care control condition and found an average percent overweight change of -0.17 ± 10.08 at 1 year. We expect some deterioration in this group at 2 years but will assume conservatively for the purpose of power computations that the two-year change will be 0 ± 10.08 in the UC group in the proposed research. Our estimated change in the FBT group begins with a review of seven studies^{20,62-67} authored by [name]. There were 314 overweight/obese children in those studies who received FBT interventions similar to the one we will employ. When we combined

the data for those 314 children, we found an overall average decrease in percent over BMI of 10.6 ± 15.3 at 24 months.

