Table 1 contains the results of the power computations using the parameters discussed above, assuming the compound symmetry covariance structure in both study arms and assuming an intraclass correlation coefficient (ICC) in the UC group of 0.01 and ICCs in the FBT group of 0.04, 0.06, 0.10, and 0.15. We assume a small ICC in the UC group of 0.01 because there is no clustering within that group meaning that the ICC should be essentially zero. While we do not have data with which to estimate the ICC in the FBT group, we note that many cluster trials that involve group interventions have reported ICCs in the 0.01 to 0.05 range. Since the PLAN intervention is individualized and since we expect PLAN children to have no contact with one another, we do not face the impact on the ICC that is present in many cluster trials. This argues for a very small ICC in the FBT group. By contrast, the fact that the same coach will be responsible for multiple children will inevitably increase the ICC above where it might otherwise be. Based on these considerations, we tabulate power for ICCs in the FBT group that range from 0.04 to 0.15. However, the many other studies that have used group interventions while yielding ICCs below 0.05 suggests that the ICC ultimately observed in PLAN will be substantially less than 0.1.

Results in Table 1 indicate that if we recruit 100% of our original target of 528 families, power will be excellent for all tabulated scenarios with an ICC in the FBT group of 0.1 or less. For an ICC

no bigger than 0.1, power remains adequate for most scenarios if we recruit at least 80% of the target (N = 432). If recruitment is below the 80% figure, an adequate power of at least 0.8 requires either the smaller of the two tabulated standard deviations or a mean difference that is at least 60% of the value observed in [name] studies (difference at least 6.4).

Table 1: Statistical power for two sided tests at the 0.05 level of significance.

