- c. If there is no clinic visit within 30 days of the 24-month target but there are visits both before and after the 24-month time point, we will interpolate linearly between predicted height and weight values at those time points to determine the predicted 24-month value. *Because we will only employ this option if height and weight data are available no more than three months before and three months after the target date for the 24-month visit, we anticipate that this interpolation approach will be performed infrequently in practice (DSMB approved protocol addenda, 11.2.18).*

3. If the 24-month value of height and/or weight is missing and the child did not have height and weight data collected by his or her pediatrician at a clinic visit that took place within 30 days of the planned 24-month assessment and did not have height and weight data measured at the clinic *within three months* both before and after the targeted 24-month visit, the 24-month value will be imputed using multiple imputation (*DSMB approved protocol addenda, 11.2.18*). Variables that will be used to facilitate the imputation process will be baseline height and weight, age, sex, and race. Any height and weight data collected using PLAN assessments at 6, 12, or 18 months will also be included in the multiple imputation.

Two points about the methods discussed in this section are in order. First, the rational for using multiple imputation only after it has been determined that clinic visit data are not available as a vehicle for imputing values is as follows. We anticipate that while values measured at the clinic will not employ the same rigor that will be employed in our protocol governed visits every six months, it is likely that the magnitude of the error will be relatively small and probably systematic rather than random within clinics. We therefore anticipate that this use of real measured data will yield more accurate results than multiple imputation. This is especially so for individuals who provide no data beyond their baseline measurement.

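### The multiple-imputation list for the primary outcome omits both treatment arm and coach, so it does not match the primary analysis model

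*Combined protocol and SAP*

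**What the plan says.** The primary analysis (Statistical Considerations, section B) is an analysis of covariance of 24-month percent over BMI on baseline and treatment. It has a random coach term that "permits between-cluster variability in the outcome measure only within the intervention group (coded as 1"). The same section states that "a proper analysis must reflect the fact that in an IRGT trial, the intervention group and the control group must use different covariance structures". Backup and floating coaches are to be accounted for when outcomes are analysed.

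Every randomised child enters that analysis. Section B.7 sets the order for a missing 24-month value: first a clinic measurement within 30 days, then interpolation between clinic visits no more than three months either side, and only then multiple imputation (item 3). The variables named for item 3 are baseline height and weight, age, sex and race, and "Any height and weight data collected using PLAN assessments at 6, 12, or 18 months will also be included in the multiple imputation". Treatment arm, coach and site are not named, and no other section brings them into the imputation. Section B.6 names PROC MI as the imputation software for the longitudinal models.

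**The concern.** Imputed values should carry the structure that the analysis model will estimate. Two parts of that structure are missing here, and they act differently.

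Without arm, a missing FBT child and a missing UC child with the same covariates receive draws from the same distribution. The imputed portion of the sample then shows little or no treatment difference, and the estimate is pulled toward zero.

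Without coach, imputed FBT children scatter around a common line and not around their own coach's mean. Observed coach means move together, the estimated coach variance falls, and the primary standard error loses part of the component that the partially clustered model was chosen to include. The effect estimate, its interval and the power of the primary test are all affected.

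**Working it through.** **Inputs from the documents**
- Test: "P-values less than 0.05 will be considered significant and all tests are two-sided" (section A).
- Sample size: power is discussed "if we recruit 100% of our original target of 528 families" (B.1). Families are told "there is a 50/50 possibility of getting one treatment over the other treatment" (Recruitment), so 264 per arm.
- Clusters: "the coach (N=3 per site) nested within the site (N=4 sites) in the FBT group" (B.1), so 12 coaches with 264/12 = 22 FBT families each.
- ICCs: "in the UC group of 0.01 and ICCs in the FBT group of 0.04, 0.06, 0.10, and 0.15" (B.1). SD 12.7 or 15.3; smallest difference 5.3.
- Missingness: the halting-rules section says power was computed for 20% dropout, with dropouts giving no data.

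**Step 1. Reproduce the plan's power.** At SD 12.7 and FBT ICC 0.10:

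SE² = (12.7²/264) × [(1 + 21×0.10) + (1 + 21×0.01)] = 0.611 × (3.10 + 1.21) = 2.633, so SE = 1.623.

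The noncentrality is 5.3/1.623 = 3.27. With 12 − 1 = 11 df, power is 0.844, against 0.85 in Table 1. The 18 cells at N = 528 with ICC 0.04-0.10 agree within 2 points. At ICC 0.15, 11 df runs up to 3.5 points high; the three cells rechecked with 8 df fit (for example 0.728 against 0.73).

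**Step 2. Weight of the coach term.** In the FBT mean, coach contributes ICC/12 and residual (1 − ICC)/264. The coach share is 0.00333/(0.00333 + 0.00364) = 48% at ICC 0.04, and 0.00833/(0.00833 + 0.00341) = 71% at ICC 0.10.

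**Step 3. What to expect with a share m imputed from baseline only.**
- Arm omitted: imputed children show no difference between arms, so the estimate tends to (1 − m) × 5.3 = 0.8 × 5.3 = 4.24.
- Coach omitted: each coach's deviation shrinks by (1 − m), so coach variance shrinks by 0.8² = 0.64, and ICC 0.10 becomes about 0.064.

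**Step 4. Simulation.** Each scenario used 1,500 trials, SD 12.7, 20% missing with baseline data only, 10 imputations and Rubin's rules. The analysis was REML with a coach effect in FBT only and arm-specific residual variance. UC ICC was set to 0. With complete data at ICC 0.10 the formula then gives √(0.611 × 4.10) = 1.583, equal to the simulated sampling SD.

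No true difference (SE/SD uses the root-mean-square SE):

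| FBT ICC | Imputation | Sampling SD | Mean SE | SE/SD | Type I |
|---|---|---|---|---|---|
| 0.04 | as listed | 1.156 | 1.357 | 1.181 | 0.026 |
| 0.04 | arm, no coach | 1.430 | 1.382 | 0.971 | 0.050 |
| 0.04 | arm and coach | 1.431 | 1.452 | 1.023 | 0.043 |
| 0.10 | as listed | 1.353 | 1.518 | 1.130 | 0.025 |
| 0.10 | arm, no coach | 1.699 | 1.539 | 0.913 | 0.065 |
| 0.10 | arm and coach | 1.693 | 1.678 | 1.002 | 0.048 |
| 0.15 | as listed | 1.476 | 1.631 | 1.115 | 0.032 |
| 0.15 | arm, no coach | 1.854 | 1.650 | 0.898 | 0.061 |
| 0.15 | arm and coach | 1.838 | 1.837 | 1.012 | 0.047 |

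With coach omitted and arm included, the estimated ICC fell from 0.10 to 0.064 and from 0.04 to 0.028, close to Step 3. The SE is below the arm-and-coach SE by 1 − 1.382/1.452 = 5%, 1 − 1.539/1.678 = 8% and 1 − 1.650/1.837 = 10%.

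True difference 5.3, ICC 0.10:

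| Imputation | Baseline only: estimate, power | With 18-month data: estimate, power |
|---|---|---|
| as listed | 4.19, 0.759 | 4.98, 0.863 |
| arm, no coach | 5.25, 0.871 | 5.35, 0.899 |
| arm and coach | 5.25, 0.821 | 5.35, 0.884 |

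The baseline-only power of 0.871 for arm without coach is not a gain, because that test exceeds its nominal level.

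**Step 5. Milder conditions at ICC 0.10.** If every dropout has 18-month data, SE/SD under no difference is 0.949 without coach and 0.970 with it, a gap of about 2%. With 5% missing from baseline only (2,000 trials) the ratios are 0.940 and 0.966, against 0.959 on complete data.

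**The case against.** A reader might infer that the plan as written gives too small a primary standard error and an anti-conservative test, because coach is missing from the imputation. The documents do not support that. The same list omits arm, and under the literal list the SE is 12-18% larger than the sampling SD and type I error is 0.025-0.032. The SE is too small only if arm is included and coach is not. Nor can the list be read as open-ended for arm but closed for coach: if unlisted variables may be assumed, the absence of coach is not established either.

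The sizes are also open to challenge, and much of that challenge stands.
- Section B.1 expects an ICC well below 0.1 and cites 0.01-0.05 from other trials. At ICC 0.04 the coach problem is small. However, the section also says there are no data for estimating the FBT ICC, and it tabulates power up to 0.15.
- The 20% figure is dropout under a worst-case assumption, not the share reaching item 3. Clinic records come first, and the group's earlier 24-month multicentre trial measured 165 of 172 children at 24 months. Section B.6 nevertheless expects more dropout here.
- Interim heights and weights already carry part of the arm and coach effects, so the shrinkage in Step 3 is a baseline-only extreme.

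Section E repeats the analysis without imputation (item 2) and fits longitudinal models to all visits (item 4). Either could expose a material discrepancy. Both are sensitivity analyses and leave the primary estimate and interval unchanged.

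**Conclusion.** The point holds as a mismatch between the imputation and analysis models, with the direction depending on how item 3 is carried out.
- Literal list: attenuation and a conservative test. In the 20%, baseline-only case at ICC 0.10, 5.3 becomes about 4.2 and power is 0.76, against 0.82 with arm and coach. With 18-month data on dropouts the estimate is 4.98 against 5.35.
- Arm added, coach omitted: SE too small by about 3-5% at ICC 0.04 with no visible type I inflation, and by about 8-10% at ICC 0.10-0.15 with type I error about 6-6.5%.

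These are upper-end sizes. They rest on assumptions that the documents do not give: data missing completely at random, equal coach caseloads, baseline SD 25, a correlation of 0.8 between 18- and 24-month change, Satterthwaite-type df, and percent over BMI imputed directly instead of height and weight. Monte Carlo error is about 0.006 on type I error and about 2% on SE ratios. Omission of arm is the larger fault. Adding arm is the natural repair, and it is then that omission of coach matters. Secondary Aim 1 adopts the same strategy for parents, so the gap carries over.

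**What to change.** In B.7 item 3, state that imputation is done separately by arm: in FBT with a two-level normal model that has a random intercept for coach, and in UC with a single-level model, keeping the variables already listed. Assign each FBT child to the same coach in the imputation as in the primary analysis, and write down the rule for children seen by backup or floating coaches. This one change repairs both omissions: in the simulations above it gave SE/SD of 1.00-1.02 with baseline-only dropouts and a mean estimate of 5.25 for a true 5.3 at ICC 0.10.

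The cost is a short SAP amendment, a coach-assignment rule, a multilevel imputation routine in place of plain PROC MI, and a somewhat wider interval than coach-blind imputation gives.

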The second point concerns the definition of a missed visit. The goal for all clinics is that PLAN participants should attend their six-month visits within \pm 30 days of the target date. However, we will not declare a given visit as having been missed until 3 months after the target date. For example, if the six-month visit has not occurred by nine months, the six-month visit will be declared to be missing and will therefore need to be imputed for analyses that include these intermediate time points. With the six-month visit having been declared missing, the next visit will be defined to be the twelve-month visit and the target date for it to occur will be twelve months after the randomization date. We recognize that a three-month difference between a scheduled visit and the actual visit is substantial, especially for growing children. But the use of this three-month difference before a visit will be declared missing will minimize the number of missed visits. Moreover, using the methods discussed in the last section of this analysis plan, we will account for any between-group differences in

time to the final study visit when we perform the primary analysis (DSMB approved protocol addenda, 11.2.18).

8. Assessing the Appropriateness of Analytic Strategies

In addition to the above concerns about covariance structures and missing data, we will routinely give careful attention to the appropriateness of the analyses we perform. For example, t-tests comparing baseline values across groups will be performed only after assessing equal variance and normality assumptions, with data transformations being pursued if assumptions are violated and Wilcoxon's test being a nonparametric alternative if an appropriate transformation cannot be found. Similar attention will be given to the appropriateness of random coefficient models where the distributional properties of variables will be evaluated and residual plots will be examined. To ensure that our conclusions are robust in the face of outlying values, sensitivity analyses that may exclude or attenuate outlying values will be pursued. The latter considerations will ensure that we are appropriately cautious about any conclusion that might have been altered if 1 or 2 subjects with outlying values had not been in the study or had had less extreme data points.

C. Analysis of Secondary Aim 1 (DSMB approved protocol addenda, 11.2.18).

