Our first step in addressing this issue will involve an assessment of whether the time to the outcome measure differs across groups. To address this question, we will compare Kaplan Meier survival curves measuring time to assessment using a generalized Wilcoxon test. The Wilcoxon test will be used instead of a logrank test because dropouts in weight loss studies tend to occur early and because the Wilcoxon test is more sensitive to early dropout than the logrank test. In performing these analyses, subjects who provide no data beyond baseline will be assumed to be on study for one month. To ensure consistency across all participants, one month will also be added to the follow-up time of children who do provide data beyond baseline. If the Wilcoxon test yields non-significant results, we will not modify our covariate-adjusted secondary analyses. If the Wilcoxon test suggests that there is a between-group difference in time to the final assessment, we will adjust for the time to the final assessment in the covariate-adjusted analyses. Similar considerations will determine whether the time to the 24 month assessment will serve as a covariate in the sensitivity analyses discussed above that involve random coefficient models, that include data collected at all intermediate time points, and that employ

statistical contrasts to compare the change from baseline to the final assessment across groups. In all of these analyses, the median time to the final follow-up along with 95% confidence bounds will be calculated.

G. Analysis of Exploratory Aim 2

Twelve PLAN coaches will be asked to participate in an audio-recorded semi-structured interview; interested coaches will provide consent over the phone and will be asked a series of questions by a trained post-doctoral researcher on the study. The questions are based on the coaches' discussions with FBT families pre-COVID and amid-COVID regarding food cost, perception, and behaviors. The telephone interviews are voluntary and will be completed based on the coaches' availability. All responses will be de-identified and aggregated with the other coaches' responses. The data will be transcribed, and summary data will be compiled. The audio file will be destroyed once the data has been transcribed and aggregated. (*DSMB approval, 5.7.2020*)

Measures to Minimize Bias

1. Enrollment and Randomization Procedures

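### The plan says the primary analysis will account for visit timing, but section F adjusts only secondary and sensitivity analyses, and its test and covariate mix dropout with visit timing

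*Combined protocol and SAP*

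**What the plan says.** Three parts of the Statistical Considerations bear on this.

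- **Section B.7, Implementation of the Intention-to-Treat Principle.** A visit is not declared missed until three months after its target date. The section concedes that such a gap is large for growing children. It defends the rule because it keeps missed visits to a minimum, and then adds a second assurance, pointing to the methods in the plan's last section. This assurance opens "we will account for any between-group differences in" and ends by naming both the quantity and the analysis: "time to the final study visit when we perform the primary analysis".
- **Section B, Primary Analysis.** Its central sentence reads: "primary analysis will be an analysis of covariance with the 24-month value as the dependent variable and with the baseline value as a predictor variable". Also in the model are the arm effect and a random coach effect in the FBT arm. It has no term for time to visit. The section then states: "All analyses other than the above are secondary or exploratory analyses".
- **Section F, The Time Between Randomization and the Measurement of the Primary Outcome.** Kaplan-Meier curves of time to assessment are compared by a generalized Wilcoxon test, chosen for its sensitivity to early dropout. For this test "subjects who provide no data beyond baseline will be assumed to be on study for one month", and one month is added to everyone else's follow-up time. The rule that follows is: "If the Wilcoxon test yields non-significant results, we will not modify our covariate-adjusted secondary analyses". If a difference is suggested, "we will adjust for the time to the final assessment in the covariate-adjusted analyses". For the random-coefficient models, "Similar considerations will determine whether the time to the 24 month assessment will serve as a covariate in the sensitivity analyses discussed above".

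Section G, on the coach interviews, now follows section F, but F is clearly the section that B.7 means.

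**The concern.** Two things look wrong.

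First, sections B.7 and F lead to different primary models. An analyst following B.7 would put a time term in the primary ANCOVA; one following B and F would not. That choice should not be open once outcomes are known by arm.

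Second, the time variable in section F does not measure what it is meant to adjust for. The ITT analysis includes every child and fills in missing 24-month values. A child with no follow-up therefore has an outcome standing for month 24 and a time of one month. For such children the covariate is a post-randomisation marker of dropout, not the timing of the measurement. The pre-test inherits the same mixture, so it can react to dropout alone, and dropout can hide a real timing difference. At stake is the meaning of the timing-adjusted secondary and sensitivity results, and whether the assurance given for the three-month tolerance is true.

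**Working it through.** **Step 1. Where time can enter.** The plan states no figure on this point, so there is none to reproduce; the sections are set side by side.

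| Analysis | Status in the plan | Time term under section F |
|---|---|---|
| ANCOVA on baseline and arm | Primary | Never |
| ANCOVA with added baseline covariates | Secondary; also sensitivity analysis 5 | Only if the Wilcoxon test suggests a difference |
| Random-coefficient models | Secondary; also sensitivity analysis 4 | By similar considerations |

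No branch of section F reaches the primary model, so the statement in B.7 has no method behind it.

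**Step 2. What the test responds to.**

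Inputs from the documents: 528 families at 1:1, so 528/2 = 264 per arm; two-sided 0.05; 20% dropout planned for; 95.9% measured at 24 months in the earlier multicenter trial, so 4.1% missing.

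If dropouts count as events and all their times fall before the completers' times, the rank variance with dropout fraction d splits into the shares 3d(1−d) for dropout status, (1−d)³ for completers' visit timing and d³ within dropouts.

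- d = 0.20: 3(0.20)(0.80) = 0.48; 0.80³ = 0.51; 0.20³ = 0.01.
- d = 0.041: 3(0.041)(0.959) = 0.12; 0.959³ = 0.88.

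At the planned dropout rate the test is about half dropout and half timing.

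**Step 3. How often it fires.** Assumptions not in the documents: completers are seen at 24 months plus a mean of 0.5 (SD 0.8), kept within 23 to 27; half of dropouts have no follow-up and the rest are last seen at 6, 12 or 18 months; the dropout splits and timing shifts are those shown. One month is added throughout, as section F requires. Rejection rates from at least 1,000 runs (censored column: 200 runs):

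| Scenario | Dropouts as events | Measured children only | Dropouts censored |
|---|---|---|---|
| 20% vs 20%, same timing | about 5% | about 4% | about 5% |
| 25% vs 15%, same timing | about 52% | about 5% | about 4.5% |
| 22% vs 18%, same timing | about 12% | about 4.5% | about 4.5% |
| 20% vs 20%, FBT 0.25 month later | about 62% | about 89% | about 92% |
| 20% vs 20%, FBT 0.5 month later | about 99% | 100% | 100% |
| FBT 25% vs UC 15%, FBT 0.25 month later | about 5% | 87 to 89% | about 88% |

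Repeat runs with other seeds and splits of last-seen visits gave 50 to 52% for the second row and 5 to 6% for the last row in the events column.

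**Step 4. How far the adjusted contrast could move.** Take 25% vs 15% dropout and assume the analysed outcomes of dropouts are 8 points worse. Let later dropouts be last seen equally often at 6, 12 and 18 months.

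- Recorded times of dropouts: 1 (half), then 7, 13, 19 (one sixth each). Mean 0.5×1 + 0.5×13 = 7.0; variance 48.
- Completers: mean 24.5 + 1 = 25.5; variance 0.8² = 0.64. Gap D = 25.5 − 7.0 = 18.5 months.
- Average within-arm variance of dropout status: (0.25×0.75 + 0.15×0.85)/2 = 0.1575.
- Within-arm variance of time: 0.1575×18.5² + 0.20×48 + 0.80×0.64 = 53.9 + 9.6 + 0.5 = 64.0.
- Slope on time, in size: 8×18.5×0.1575/64.0 = 0.364 point per month.
- Arm difference in mean time: 0.10×18.5 = 1.85 months.
- Shift in the arm contrast: 0.364×1.85 = 0.67 point, or 0.67/5.3 = 13% of the smallest planned difference.

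With later dropouts weighted to the earlier visits (25%, 15% and 10% of all dropouts at 6, 12 and 18 months) the same formula gives 0.71. A simulated linear adjustment gave 0.67 and 0.70 under the two patterns. These are upper values, because the full 8-point gap is placed in the analysed outcomes.

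**The case against.** The strongest reply is that little depends on this. Section F leaves the primary ANCOVA alone, so the confirmatory contrast is what section B says it is. That stands. A reader might infer that the primary result is biased by the timing rule; the documents do not support that.

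A reader might also infer that the Wilcoxon test is simply a dropout test. That goes too far. At 20% dropout, timing carries about half the rank variance, and a half-month shift with equal dropout is found about 99% of the time. Kaplan-Meier and generalized Wilcoxon methods also allow censoring. With dropouts censored, a pure dropout difference rejects at about the nominal rate. The remark on sensitivity to early dropout, and the one-month value, make more sense if dropouts are events, but the plan does not say.

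It is also tempting to multiply a 10-point dropout difference by 8 points and claim a 0.8-point shift. A linear time term does not absorb the whole gap. The plan's multiple imputation, from baseline size, age, sex, race and any intermediate visits, would also draw children with baseline data only towards values like those of completers. A trial calculation with a simplified form of that imputation, under an assumed intermediate-visit signal and with no chart data, put the shift at 0.1 to 0.2 point.

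Three smaller replies are fair. B.7's first reason for the three-month tolerance is fewer missed visits, not the timing adjustment. The outcome is relative to age- and sex-specific norms, which removes the normal-growth part of late measurement. Finally, an ungated time term in the primary model would also reconcile the text. None of these removes the disagreement between the sections.

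**Conclusion.** The point holds in a limited form. B.7 attributes to the primary analysis a timing adjustment that neither section B nor section F provides; this rests on the text alone. Section F's test and covariate also mix dropout with visit timing, and the handling of dropouts as events or censored is undefined.

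The size depends on that undefined choice and on the arm difference in dropout. With dropouts as events, false firing ranges from about 12% (22% vs 18%) to about 52% (25% vs 15%), and a real 0.25-month shift can be almost fully masked. With dropouts censored, or with equal dropout, false firing stays near 5%. The consequence is confined to timing-adjusted secondary and sensitivity results: at most about 0.7 point under the assumed 8-point gap, and less after multiple imputation. The dropout splits, visit-time distribution and 8-point gap are all assumptions. It should be corrected before analysis, but it does not threaten the primary conclusion.

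**What to change.** 1. In B.7, replace the assurance with a statement that the primary ANCOVA is not adjusted for visit time and that timing is examined in a sensitivity analysis. This keeps the primary model as specified in section B and as simulated for power.
2. In section F, drop the Wilcoxon pre-test and the last-seen time variable. Compare time from randomisation to the actual 24-month measurement, by arm, among measured children only.
3. Pre-specify one sensitivity version of the primary ANCOVA with that time as a covariate, set to 24 months for values imputed at 24 months. Run it whatever the comparison shows.
4. Report dropout by arm, and its timing, as a separate result.

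The cost is a few sentences of SAP text and one extra run. The downside is that the extra model adjusts for a post-randomisation variable, so it should be labelled as sensitivity only. No sample size or power figure changes.
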